#### 8.4 VARIABLES

#### 8.4.1 Exposures

The exposure measures are based on pharmacy dispensings of the two long-acting bronchodilators under study, namely fixed-dose combination of Tio+Olo and a fixed-dose combination of LABA and ICS, over one year of follow-up. As described in the data analysis section, the as-treated analysis, which is the main analysis, will consider exposure as current use of Tio+Olo or LABA/ICS within the treated groups defined as within the days supply recorded at the time of pharmacy dispensing, allowing for a gap between dispensings of up to 15 days. This gap is allowed in consideration of plausible delays in obtaining medication refills and continued use beyond the days supplied where medication has been missed due to imperfect adherence, and will be varied in sensitivity analyses (see Section 8.9.2). The treatment segment ends at the earliest of the following events:

- 1. Fifteen days after the end of the observed days supply for the medication received on the index date without a subsequent dispensing of COPD medication (i.e., discontinuation)
- 2. Initiation of triple therapy (i.e., addition of ICS to Tio+Olo or a LAMA to LABA/ICS (i.e., treatment escalation)
- 3. Any other change in use of study medication by active ingredient, inclusive of a change to a different combination therapy, change from a fixed form to a free form combination therapy, or a change from combination therapy to monotherapy (i.e., switch)

Changes in dose for medications started on the index date will not impact the end of the treatment segment. Codes used to identify study medications are included in Annex 3.1.

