#### 8.4.2.2 Secondary outcome(s)

The first secondary outcome is time to first hospitalization for community-acquired pneumonia (serious pneumonia). Pneumonia will be defined using ICD-9-CM diagnoses 481.x-486.x; 487.0, 507.x, 507.0, 507.1, 507.8, 510.0, 510.9, 511.0, 513.0, 514.x, 517.1, 519.8, 530.84, and ICD-10 diagnosis codes J10.0; J11.0; J12-J18; J22; J69; J85.0; J85.1; J86. This definition has been used successfully in COPD [P07-09514; P16-10095].

The second secondary outcome is time to a pharmacy dispensing indicating escalation to triple therapy, (i.e., addition of ICS to Tio+Olo or a LAMA to LABA/ICS).

The third secondary outcome is time to an adverse outcome including exacerbation, hospitalization for pneumonia, and escalation to triple therapy, defined as time from cohort entry until the earliest primary or secondary outcome as defined above (See Section 8.4.2.1, 8.4.2.2).

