### **ANNEX 3.1: DEFINITION OF STUDY EXPOSURES**

See section 8.4.1. Complete list of drug codes will be added to this document after review and approval.

Medication	HCPCS	GPI
LABA (single)		
Indacaterol		44201042X
Salmeterol		4420105810X
Formoterol	J7605, J7606, J7640, Q4099	44201027X 44201012102520
Olodaterol		44201052X
LAMA (single)		
Tiotropium		44100080X
Aclidinium		44100007X
Glycopyrronium	J7642, J7643	44100020X
Umeclidinium		44100090X
Revefenacin		44100075002020
ICS (single)		4440X 4220X
Fluticasone	J7641	44400033X
Budesonide	J7626, J7627, J7633, J7634	44400015X
Beclomethasone	J7622	42200010x 44400010x
Mometasone		42200045101820 44400036X
Flunisolide	J7641	44400030X
Ciclesonide		4440001700x
Dexamethasone		4440002010x
Triamcinolone	J7683, J7684	4440004020x

LABA/LAMA		
Formoterol/glycopyrroni um	44209902543	220
Indacaterol/glycopyrroni um	44209902600	110
Vilanterol/umec lidinium	4420990295X	
Olodaterol/tiotropium	4420990292X	
LABA-ICS		
Fluticasone furoate/salmeterol	4420990270	
Fluticasone furoate/vilanterol	4420990275	
Mometasone/formoterol	4420990290	
Budesonide/formoterol	44209902413	

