### **ANNEX 3.3: DEFINITIONS OF STUDY COVARIATES**

See section 8.4.3. Complete list of codes will be added to this document after review and approval.

Medication	HCPCS	GPI
Short-acting beta- agonists		
Levalbuterol	J7617J7607J7612, J7614,J7615	4420104510X 4420104550X
Albuterol	J7602, J7603, J7609-J7611, J7613, J7616, J7620, J7625, Q4093, Q4094	4420101000X 4420101010X
Terbutaline	J3105J7680,J7681	442010602X
Isoproterenol	J7657 J7658 J7659	44201040X

	J7660	
Methylxanthines		
A minanhyllina		4430001000x
Aminophylline		4430001010x
		4430004000x 499100240X 4499100220X
		4499100242X 4499100250X 44992203X
Theophylline (SR)	J2810	44993003X 44993204X 44999003X
		44999602X 4499220310X 4499960270X
		4499220315X
SAMA (Short-acting muscarinic antagonists)		
Ipratropium bromide	J7644, J7655	4230X 44100030X
Antibiotics for a respiratory condition		
Aamikacin	J0278	07000010x
Amoxicillin/potassium clavulanate		0199000220x
Amoxicillin		01200010x
Ampicillin	J0290	01200020x
Ampicillin-sulbactam	J0295	0199000225x
Azithromycin	J0456	03400010x
Aztreonam	S0073	16000005x
Cefaclor		02200040x
Cefdinir		02300040x
Cefepime	J0692	02400040x
Cefixime		02300060x
Cefotaxime	J0698	02300075x
Cefpodoxime		02300065x
Cefprozil		02200062x
Ceftazidime	J0713, J0714	02300080x
Ceftriaxone	J0696	02300090x

c31403012-01

Cefuroxime	J0697	02200065x
Ciprofloxacin	J0744	05000020x
Clarithromycin		03500010x
Doxycycline		04000020x
Ertapenem	J1335	16150030x
Erythromycin	J1364	0310x
Gemifloxacin		05000083x
Imipenem	J0743	16159902x
Levofloxacin	J1956	05000034x
Linezolid	J2020	16230040x
Meropenem	J2185	16150050x
Moxifloxacin	J2280	05000037x
Penicillin G benzathine	J0561, J0558	01990002x, 01100020x
Penicillin VK		01100040x
Piperacillin	S0081	01400040x
Piperacillin-tazobactam	J2543	019900027x
Procaine penicillin	J0558, J2510	
Ticarcillin		01400050x
Ticarcillin-clavulanate	S0040	019900023x
Trimethoprim- sulfamethoxazole	S0039	169900023x
Vancomycin	J3370	16000060102x

Condition	ICD9	ICD10	ICD9 proc	ICD10 proc	HCPC S	CPT
Asthma	493	J45				
	493	J45.2				
	493	J45.20				
	493.01	J45.21				
	493.02	J45.22				
	493.1	J45.3				
	493.1	J45.30				

		<del> </del>	1	1	1	1
	493.11	J45.31				
	493.12	J45.32				
	493.2	J45.4				
	493.2	J45.40				
	493.21	J45.41				
	493.22	J45.42				
	493.8	J45.5				
	493.81	J45.50				
	493.82	J45.51				
	493.9	J45.52				
	493.9	J45.9				
	493.91	J45.90				
	493.92	J45.901				
		J45.902				
		J45.909				
		J45.99				
		J45.990				
		J45.991				
		J45.998				
Lung cancer	162	C33				

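### Annex 3.1 lists 4220-prefix codes as single ICS; if these are not orally inhaled products, one fill creates a false escalation event, and only in the Tio+Olo arm

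*Combined protocol and SAP*

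**What the plan says.** Section 8.4.1 sends the reader to Annex 3.1 for drug identification: "Codes used to identify study medications are included in Annex 3.1". The single-ICS block of that annex opens with two class-level prefixes, 4440X and 4220X. Two ingredients then appear under both: beclomethasone ("42200010x 44400010x") and mometasone ("42200045101820 44400036X"). Annex 3.3 does something similar for ipratropium: "4230X 44100030X". The annex also states: "Complete list of drug codes will be added to this document after review and approval".

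The ICS list feeds two rules. In Section 8.4.1 the treatment segment ends on "Initiation of triple therapy (i.e., addition of ICS to Tio+Olo or a LAMA to LABA/ICS (i.e., treatment escalation". Section 8.4.2.2 lists escalation second among the secondary outcomes, as "time to a pharmacy dispensing indicating escalation to triple therapy, (i.e., addition of ICS to Tio+Olo or a LAMA to LABA/ICS". Escalation is also one component of the third secondary outcome, the composite. Neither section sets a condition on route, indication or repeat fills.

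**The concern.** A steroid that is not inhaled into the lungs does not turn a LABA/LAMA regimen into triple therapy. If the 4220 entries are such products, the programmed definition would still record an escalation on the day of the fill.

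The definition of escalation differs by arm, so the error would too. An ICS code triggers it on Tio+Olo, and a LAMA code triggers it on LABA/ICS. False events would therefore accumulate in one arm of a secondary outcome and of the composite. Weighting on baseline propensity scores does not remove misclassification of an outcome during follow-up. Section 8.4.2.1 itself treats loss of outcome specificity as a worse threat than a non-differential loss of sensitivity; here the loss of specificity would also be differential.

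**Working it through.** The plan states no figure on this point, so there is nothing to reproduce. The check has four steps.

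**1. Inventory of GPI codes (Annexes 3.1 to 3.3).**
- Single ICS: 12 entries. Three start with 4220 (4220X, 42200010x, 42200045101820) and nine with 4440.
- LAMA: five entries, all starting with 4410.
- Every LABA and combination GPI code in Annex 3.1 starts with 44.
- Prednisolone, listed in Annex 3.2 with the outcome codes, is under 22.
- Ipratropium has one entry under 4410 and one class-level entry, 4230X.

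The leading digits thus separate corticosteroids into groups 22, 42 and 44. Group 44 holds all the inhaler products in Annex 3.1. Beclomethasone, mometasone and ipratropium already have a group 44 code. A second code under 42 suggests a different product form. That this form is nasal is an assumption to be confirmed in the GPI dictionary.

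**2. Where a 4220 fill takes effect.**
- Tio+Olo, follow-up: it meets the escalation rule, so it is an event for escalation and the composite, and it ends follow-up for exacerbation and pneumonia.
- LABA/ICS, follow-up: it cannot meet the escalation rule, because no LAMA GPI code starts with 42. It could still end the segment under the rule on other changes by active ingredient.
- Either arm: it could count as a COPD medication under the discontinuation rule. It can also enter Exclusion 3 (prior free combinations), the ICS monotherapy covariate in Section 8.4.4, and the sensitivity analysis that accepts free LABA/ICS.
- The 4230X entry affects the short-acting muscarinic covariate.

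**3. Size for escalation and the composite (all rates assumed).** Take constant hazards, a true HR of 1.0, a true event rate r per year in both arms, and a 4220 fill rate n per year on Tio+Olo. Then

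apparent HR = (r + n) / r = 1 + n/r.

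| Escalation rate r | n = 0.03 | n = 0.05 | n = 0.10 |
|---|---|---|---|
| 0.10 | 1.30 | 1.50 | 2.00 |
| 0.20 | 1.15 | 1.25 | 1.50 |
| 0.30 | 1.10 | 1.17 | 1.33 |

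For the composite, with a base rate of 0.4 to 0.8 per year, the range runs from 1 + 0.03/0.8 = 1.04 to 1 + 0.10/0.4 = 1.25.

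On the risk scale, suppose a one-year escalation risk of 10% and a one-year fill risk of 5%. The hazards are −ln(0.90) = 0.1054 and −ln(0.95) = 0.0513, so the apparent HR is 1 + 0.0513/0.1054 = 1.49. Applied to the 5,469 Tio+Olo users in Section 8.7, the net extra patients counted as escalated are 5,469 × (0.90 − 0.90 × 0.95) = 246. With escalation risks of 5% to 20% and fill risks of 2% to 10%, the apparent HR runs from 1.09 to 3.05 and the extra patients from 88 to 520. The counts assume a full year on treatment, so shorter follow-up would lower them.

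**4. Size for the primary outcome.** The fill only censors. With λ = −ln(1 − fill risk), the share of one-year Tio+Olo person-time lost is 1 − (1 − e^(−λ))/λ. Fill risks of 2%, 5% and 10% give losses of 1.0%, 2.5% and 5.1%.

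**The case against.** The strongest reply is that the documents never say what prefix 4220 means. The word nasal does not appear, and no GPI dictionary is attached. This stands: the documents establish the anomaly of two prefixes, not the route. A reader might infer that the plan demonstrably counts nasal sprays as triple therapy; the documents alone do not prove that.

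A second reply is that the list is provisional, since a complete one is to follow review and approval. This stands in part. Review could remove entries, but the annex speaks only of adding codes. The milestones put extraction and coding from August 2019 and preliminary results in December 2019, both before this version of February 2020. The printed list may already have been used, though nothing shows that it was.

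A third reply is that the codes do not act in one arm only. This also stands. The one-arm statement is true of false escalation events during follow-up. It does not hold for the exclusion, the covariate, or the switch and continuation rules.

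Finally, every rate in the size calculation is assumed, and an HR of 2.00 requires fills as frequent as true escalations (n = r = 0.10). That is correct, and the figures serve only to show scale. The direction does not depend on them.

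**Conclusion.** The point holds conditionally. Three of the 12 single-ICS GPI entries belong to a prefix group that looks distinct from the inhaled products. If the lookup confirms that they are not orally inhaled, the escalation and composite hazard ratios are biased against Tio+Olo. With assumed rates of r = 0.20 and n = 0.05 per year, the apparent escalation HR is 1.25 when the truth is 1.0. The actual size depends on fill rates that the documents do not give.

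Two stronger readings should be resisted. One is that the primary hazard ratio is biased. The plan's rules produce only extra censoring there and in the pneumonia analysis, and that biases the estimate only if it is informative. The other is that follow-up is shortened in one arm alone. The switch rule could also censor a LABA/ICS user on a 4220 fill, so this is not established.

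**What to change.** 1. Look up the route of 4220X, 42200010x, 42200045101820 and 4230X in the GPI dictionary, and print product labels beside the codes.
2. Restrict the ICS list in Annex 3.1 and the ipratropium list in Annex 3.3 to orally inhaled products, and remove the 4220 and 4230 entries once they are confirmed as not inhaled. Removal should follow confirmation, because deleting an inhaled product would lose true escalations.
3. Rebuild escalation, the composite, censoring, Exclusion 3, the affected covariates and the free LABA/ICS sensitivity analysis from the corrected list.
4. State whether the preliminary results used the printed list, and rerun them if so.

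The cost is one lookup, a code-list edit and a rerun. No new data are needed.

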#### **8.4.2 Outcome(s)**

#### 8.4.2.1 Primary outcome(s)

The primary outcome event for effectiveness is time to first COPD exacerbation after cohort entry. The event is defined as follows:

• Severe exacerbation:

Proprietary confidential information © 2020 Boehringer Ingelheim International GmbH or one or more of its affiliated companies

- o Hospitalization with a principal discharge diagnosis of COPD.
- Moderate exacerbation:
  - o An ED visit with a discharge diagnosis of COPD, and/or
  - An antibiotic for a respiratory condition dispensed the same day as an oral corticosteroid

Time to the first COPD exacerbation will be measured from cohort entry until the occurrence of a hospitalization for COPD (severe exacerbation) or ED visit for COPD or prescription of an antibiotic and an oral corticosteroid on the same day (moderate exacerbation). Severe and moderate exacerbations will be considered as a composite for main analyses. Sensitivity analyses will stratify by exacerbation severity.

Although there is precedent for defining moderate exacerbation based on use of antibiotics for a respiratory infection without requiring concomitant oral corticosteroids, we have chosen a more restrictive definition of exacerbation. Because diagnoses listed on outpatient claims often correspond to a patient's past medical history in addition to acute problems, we expect limited ability to capture the indication for which antibiotics are prescribed. As such, including antibiotics alone as a case definition for exacerbation would introduce potentially substantial misclassification of outcome where antibiotics were truly given for non-respiratory infections. Given that our analyses will yield estimates on a ratio measure, non-differentially reduced sensitivity is a less important threat to validity than reduction of outcome specificity, which produces an expectation of bias towards the null hypothesis. In order to test our assumptions that the sensitivity of our outcome definition is not differential between the Tio+Olo and LABA/ICS groups, we would produce counts of patients with antibiotics alone during follow-up, and determine whether the proportion of potential exacerbations that we excluded through this design decision is comparable across groups.

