#### *Inclusion Criteria:*

- 1. At least one prescription for Tio+Olo combined inhaler or a LABA/ICS combined inhaler between 1 January 2013 and 31 March 2019.
  - a) The first dispensing of either Tio+Olo or LABA/ICS combined inhaler will be defined as the index date.
  - b) For the main analyses, only fixed dose combination (FDC) inhalers will be included. Sensitivity analyses will also accept free combinations of LABA/ICS.
- 2. At least one diagnosis of COPD at any time prior to the index date.
- 3. At least one year of continuous medical and pharmacy health plan eligibility prior to the index date will be required to allow a baseline period for the covariates and identification of new use of the study drugs.

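### Section 8.4.2.1 sets no diagnosis position for ED visits, so a visit for another cause with COPD listed as history can count as a primary event; the hazard ratio moves towards 1 only if such visits are unrelated to treatment

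*Combined protocol and SAP*

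**What the plan says.** Section 8.4.2.1 defines the primary event as the first COPD exacerbation, reached by one of three routes.

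- **Severe:** "Hospitalization with a principal discharge diagnosis of COPD".
- **Moderate, ED route:** "An ED visit with a discharge diagnosis of COPD, and/or" the drug route.
- **Moderate, drug route:** a respiratory antibiotic and an oral corticosteroid dispensed on the same day.

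A restatement in the same section speaks of an "ED visit for COPD or prescription of an antibiotic and an oral corticosteroid on the same day". It suggests that COPD is the reason for the visit but gives no rule on position. The routes are pooled: "Severe and moderate exacerbations will be considered as a composite for main analyses".

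The section also explains why antibiotics alone do not count. It says that "diagnoses listed on outpatient claims often correspond to a patient's past medical history in addition to acute problems", and that the more serious threat is a "reduction of outcome specificity, which produces an expectation of bias towards the null hypothesis".

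Cohort entry (Section 8.3, inclusion criterion 2) requires "At least one diagnosis of COPD at any time prior to the index date". The COPD list in Annex 3.2 contains chronic codes such as 496 and J44.9 together with acute ones (491.21, 491.22, J44.0, J44.1). The annex says that the full list is still to be added.

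**The concern.** The word principal stands in the hospital criterion and is missing from the ED criterion. A programmer working from this text has no ground to reject an ED claim on which COPD is a secondary code. In a cohort selected on a chronic diagnosis, a secondary COPD code says little about why the patient came. A visit for a fall or for chest pain, with 496 or J44.9 carried along as history, would qualify.

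The section's own argument about history codes and specificity applies equally to this route, but the section does not carry it over.

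The primary hazard ratio is at stake. So is the third secondary outcome (Section 8.4.2.2), because the primary event is one of its components.

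**Working it through.** **1. The plan's own figure.** Section 8.7 cites an analysis of another database in which 2,000 patients per cohort gave over 90% power at a hazard ratio of 0.85. By Schoenfeld's formula with 1:1 allocation and two-sided alpha 0.05 (assumed from the 95% confidence intervals):

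events = 4 × (1.960 + 1.282)² / (ln 0.85)² = 1,592

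That is 1,592 / 4,000 = 40% of patients with an event. The documents give no event proportion, so the figure can be neither reproduced nor refuted. It serves below only as an illustrative true effect.

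**2. Dilution if the extra visits are unrelated to treatment.** Let f be the share of first events in the LABA/ICS arm that are ED visits for other causes, equally frequent per person-time in both arms. Then:

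observed HR = (1 − f) × true HR + f

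| f (assumed) | Observed HR when the true HR is 0.85 |
|---|---|
| 10% | 0.9 × 0.85 + 0.1 = 0.865 |
| 20% | 0.8 × 0.85 + 0.2 = 0.880 |
| 30% | 0.7 × 0.85 + 0.3 = 0.895 |
| 40% | 0.6 × 0.85 + 0.4 = 0.910 |

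Here f is the ED share of first events times the false share among those ED events. The documents give neither. The upper end is demanding: f = 40% needs, for example, ED visits to be 60% of first events and two-thirds of those to be false.

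**3. What changes if some of the visits are for pneumonia.** Section 6 links ICS use to pneumonia but gives no rate. Assume a pneumonia rate ratio of 1.5 for LABA/ICS against Tio+Olo, and let p be the pneumonia share of the false events in the LABA/ICS arm:

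HR of the false events = (1 − p) + p / 1.5 = 1 − p/3

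- p = 20% gives 0.933. With f = 20% and a true HR of 0.85, the observed HR is 0.8 × 0.85 + 0.2 × 0.933 = 0.867: still towards 1, but less than the 0.880 above.
- The pull reverses when 1 − p/3 is below 0.85, that is when p exceeds 45%.
- If the true HR is 1, the same mix (f = 20%, p = 20%) gives 0.8 + 0.2 × 0.933 = 0.987, a small apparent benefit of Tio+Olo.

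**4. Power in the expected cohort.** Section 8.7 expects 5,469 Tio+Olo and 53,432 LABA/ICS patients: 58,901 in all, 9.3% on Tio+Olo. Event proportions are assumed. Schoenfeld power, ignoring any precision lost to weighting:

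| Patients with an event | f = 0 | f = 20% | f = 30% |
|---|---|---|---|
| 20% | 99.9% | 98.1% | 93.8% |
| 10% | 95.2% | 81.3% | 69.5% |

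These rows hold the number of counted events fixed, whereas the restricted definition would also count fewer. At 10% with an event (5,890 events) and f = 20%, removing the false ones leaves about 0.8 × 5,890 = 4,712. At HR 0.85 that gives about 90% power, against 81.3% for the unrestricted composite. In this scenario the restriction does not cost power.

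**The case against.** Several stronger readings are tempting, and the documents do not support them.

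- **That the protocol adopts an any-position rule.** It never says so, and its restatement as an ED visit for COPD can be read as the reason for the visit. What the text establishes is that no position is specified.
- **That the estimate must be diluted.** A reader might infer this because the section itself equates lost specificity with bias towards the null. That holds only for false events that are largely unrelated to treatment. Pneumonia under ICS is an evident exception, as step 3 shows.
- **That the code list holds no acute codes.** It does hold them; it is simply not limited to them, and it is provisional.
- **That an ED visit ending in admission for another principal diagnosis returns as a moderate event.** No section says how such visits are counted.
- **That the loose rule also defines baseline exacerbation history.** Section 8.4.4 lists ED visits as moderate events without any diagnosis rule, so the history is undefined on this point and the link is an inference.

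Two further objections carry weight. First, the planned analysis by severity will give a severe-only result based on principal diagnoses. This is a useful check, but it drops every moderate event and does not repair the composite. Section 8.4.1 also refers to sensitivity analyses in a Section 8.9.2 that is not in the text available, so nothing is concluded from its absence. Second, a first-listed rule may miss real exacerbations coded with pneumonia first. If pneumonia is more frequent under LABA/ICS, that loss is differential, whereas the section accepts only non-differential loss of sensitivity. This objection stands and shapes the fix.

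**Conclusion.** The point holds as a gap in the definition of the primary endpoint: no position is required of the ED diagnosis, in a cohort where a COPD code is universal, and against the section's own reasoning on specificity. Taken literally, ED visits for other causes enter the composite.

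The size cannot be derived from the documents. Under an assumed false share of 10% to 40%, no relation to treatment, and an illustrative true hazard ratio of 0.85, the observed value is 0.865 to 0.91. At 30%, a 15% reduction reads as about 10%. Towards 1 is the conditional direction, not an established one. In the full cohort the main harm is a biased estimate; loss of power matters chiefly at low event proportions and in the smaller eosinophil and exacerbation-history strata.

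The definition should be settled before the analysis is run.

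**What to change.** In Section 8.4.2.1, define the ED criterion as an ED visit with COPD as the principal (first-listed) discharge diagnosis, matching the hospital criterion. In Section 8.4.4, state that the same rule applies to the ED component of baseline exacerbation history. Report the composite under the unrestricted ED definition as a sensitivity analysis. As an addition, tabulate by arm the ED visits that qualify only through a secondary COPD code, with their first-listed diagnosis. This would give the share f and show whether pneumonia accounts for a treatment difference.

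The cost is a short change of wording and one further run on the same claims. The drawback is fewer events and some lost sensitivity, possibly differential where exacerbations are coded with pneumonia first. For that reason both versions should be reported: close agreement would indicate that the position rule matters little, and a gap would show its effect.

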#### 6. RATIONALE AND BACKGROUND

Chronic obstructive pulmonary disease (COPD) is a leading cause of morbidity and mortality throughout the world [P07-11503]. It has recently risen to become the third leading cause of death in the US [R13-1383]. Long-acting bronchodilator medications, that include long-acting beta2-agonists (LABAs) and the long-acting muscarinic antagonists (LAMAs) such as the anticholinergic tiotropium, have become central maintenance therapy to the management of COPD, with inhaled corticosteroids (ICS) added with increasing severity [P07-11503].

The treatment of COPD increasingly involves multiple therapies including long-acting bronchodilators (LAMAs and LABAs) and inhaled corticosteroids (ICS) with combinations of these drugs now formulated into single inhalers. Optimal treatment choice appears to be influenced by a variety of factors including exacerbation risk. Although the use of ICS has increased disproportionately with respect to COPD treatment guidelines, it may be appropriate only in a subset of these users [P15-12888; P16-12287]. For example, the recent FLAME randomized trial reported that patients receiving the LABA/LAMA combination had fewer exacerbations than those receiving the LABA/ICS combination over a one-year follow-

Proprietary confidential information © 2020 Boehringer Ingelheim International GmbH or one or more of its affiliated companies

up period. In the WISDOM trial, in patients on triple therapy the risk of moderate or severe exacerbations was similar among those who discontinued and those who continued ICS. The ENERGITO study showed significant improvements in lung function with the LAMA/LABA FDC Tio+Olo versus LABA/ICS. Further, pneumonia associated with long-term ICS use increases the risk of hospitalization, and is associated with substantial increases in cost [P07-09514; R18-2874].

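### The antibiotic-plus-steroid route to a moderate exacerbation does not exclude pneumonia, so false primary events may differ between groups and need not bias towards the null

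*Combined protocol and SAP*

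**What the plan says.** Section 8.4.2.1 gives three routes to a primary event. A severe event is a hospital stay with COPD as the principal discharge diagnosis. A moderate event is either "An ED visit with a discharge diagnosis of COPD, and/or" the dispensing route, "An antibiotic for a respiratory condition dispensed the same day as an oral corticosteroid". On the main analysis it says: "Severe and moderate exacerbations will be considered as a composite for main analyses". Annex 3.3 defines the respiratory antibiotics by drug codes, with no diagnosis attached.

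The same section explains why antibiotics alone were rejected: "we expect limited ability to capture the indication for which antibiotics are prescribed", and some would be given for non-respiratory infections. It treats non-differential loss of sensitivity as a lesser threat than "reduction of outcome specificity, which produces an expectation of bias towards the null hypothesis". To check that sensitivity does not differ between groups, it says "we would produce counts of patients with antibiotics alone during follow-up". It also plans sensitivity analyses by exacerbation severity.

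Section 8.4.2.2 makes pneumonia an outcome only when it leads to hospital admission. Section 6 states that "pneumonia associated with long-term ICS use increases the risk of hospitalization", and the abstract reports that stopping ICS was associated with a lower pneumonia risk.

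**The concern.** The steroid requirement is defended as protection against counting non-respiratory infections. Pneumonia is a respiratory infection, so that defence does not cover it. A patient treated for outpatient pneumonia with an antibiotic and an oral steroid on the same day is recorded as having a COPD exacerbation, and the case cannot appear under the pneumonia outcome because that requires admission. It also enters the third secondary outcome as an exacerbation.

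False positives pull the HR towards 1 only if they occur at the same rate in both groups. The protocol's own rationale gives a reason to doubt this, because only the comparator contains an ICS. The planned check looks at events the definition left out. It does not look at events wrongly let in.

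At stake is how the primary HR is read. Part of an apparent exacerbation advantage for Tio+Olo could be a pneumonia difference, in a direction that the protocol's text would lead readers to think impossible.

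**Working it through.** The plan gives no false-positive figure to reproduce. Its one numerical statement on the primary outcome, in Section 8.7 (2,000 per cohort, HR 0.85, over 90% power), is unaffected by this point.

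**Model.** Let the LABA/ICS hazards be *a* for true exacerbations and *b* for pneumonia counted as exacerbation, both constant over time. Let *s* = *b*/(*a* + *b*), the share of all recorded LABA/ICS events that are really pneumonia. With HR_true for exacerbation and HR_p for pneumonia (both Tio+Olo relative to LABA/ICS):

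HR_obs = (HR_true × *a* + HR_p × *b*)/(*a* + *b*) = (1 − *s*) × HR_true + *s* × HR_p

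The observed HR is a weighted average, so false events pull it towards HR_p. That is a pull towards 1 only when HR_p = 1.

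**Inputs.** The documents give neither *s* nor HR_p. Assumed ranges: *s* = 5% to 20%, HR_p = 0.60 to 0.75.

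**Size with HR_true = 1.0.**

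| *s* | HR_p = 0.75 | HR_p = 0.60 |
|---|---|---|
| 5% | 0.95 + 0.0375 = 0.9875 | 0.95 + 0.03 = 0.98 |
| 20% | 0.80 + 0.15 = 0.95 | 0.80 + 0.12 = 0.92 |

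Here *s* is a share of all events. If the dispensing route supplied half of them (assumed), 5% to 20% overall would mean 10% to 40% of that route's events.

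**Direction, with *s* = 10%.**

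- HR_true 0.85, HR_p 1: 0.765 + 0.100 = 0.865. This is the plan's case, towards the null.
- HR_true 0.85, HR_p 1/1.2 = 0.833: 0.765 + 0.083 = 0.848, almost no bias.
- HR_true 0.85, HR_p 0.90: 0.765 + 0.090 = 0.855, a small rise.
- HR_true 1.10, HR_p 1/1.5 = 0.667: 0.990 + 0.067 = 1.057, lower, but nearer to 1.

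So HR_obs is below HR_true exactly when HR_p is below HR_true.

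**Why small shifts can matter.** Section 8.7 expects 5,469 Tio+Olo and 53,432 LABA/ICS users, 58,901 in all, a Tio+Olo share of 0.0929. The standard error of the log HR is about 1/√(*E* × 0.0929 × 0.9071), where *E* is the number of events. If 20% to 40% of patients have an event (assumed), this is 0.0317 to 0.0224. With HR_true = 1, the chance of a two-sided p < 0.05 rises from 5% to 8%–12% at HR_obs 0.983 (for example *s* = 5%, HR_p = 0.667) and to 37%–63% at HR_obs 0.950 (*s* = 20%, HR_p = 0.75). This ignores the propensity weighting and uses preliminary counts that do not show the asthma and lung-disease exclusions, so it probably overstates the precision.

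**The case against.** Several stronger readings are tempting, and the documents do not support them.

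- A reader might infer that moderate exacerbations in general need no diagnosis. The emergency-department route requires a COPD diagnosis, and the severe route a principal one. Only the dispensing route is exposed.
- A reader might infer that all outpatient pneumonia is counted as exacerbation. Cases without a same-day oral steroid are not, and that requirement is a deliberate specificity safeguard which should keep *s* down. Some antibiotic-only pneumonia would also appear in the planned counts by group, so those counts could hint at a difference indirectly.
- A reader might infer that an excess with LABA/ICS is established. The rationale concerns long-term ICS use and gives no rate ratio. The cohort is new users, analysed as treated and for one year. The excess is plausible, not shown.
- A reader might infer that the bias always moves the HR away from 1 in favour of Tio+Olo. The working shows otherwise.
- A reader might infer that no relevant analysis is planned. Section 8.4.1 refers to Section 8.9.2 for sensitivity analyses, and that section is not in the text available for review, so such an analysis cannot be ruled out.

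It can also be said that the bias sentence, read whole, is about non-differential error, so rewording it is mostly editorial. That has force, but the sentence attaches the qualifier to sensitivity and not to specificity. Sections 8.6 and 8.11 do acknowledge outcome misclassification in general terms. The severe-only result avoids the dispensing route, but it neither measures nor corrects the error in the composite.

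The objection to the remedy stands. Section 8.4.2.1 itself notes that outpatient diagnoses often reflect past history. If pneumonia is more common with LABA/ICS, a filter on pneumonia codes may remove more true exacerbations there. For illustration (assumed), with a true HR of 1 and 10% of LABA/ICS but 6.7% of Tio+Olo true events dropped, the result is 0.933/0.900 = 1.04, an error in the opposite direction.

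**Conclusion.** The point holds for the dispensing route. That route lets outpatient pneumonia treated with both drugs into the primary composite. Equal false-positive rates cannot be taken for granted given the protocol's own rationale, and the planned antibiotic-only count does not test for inequality. The expectation of bias towards the null is therefore justified only for non-differential error.

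The size is unknown. The range of about 0.92 to 0.99 for the observed HR rests on a true HR of 1.0, constant hazards, and assumed values for the pneumonia share and the pneumonia HR. At the low end the effect is negligible. The documents support a possible lowering of the HR, conditional on the pneumonia HR being below the true exacerbation HR. They do not support a claim that the primary result will be biased in favour of Tio+Olo. This is a modest, inexpensive improvement and not a reason to change the primary definition.

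**What to change.** 1. In Section 8.4.2.1, limit the statement about bias towards the null to specificity loss that is equal in both groups.
2. Extend the check already planned there: report, by treatment group, the number and share of dispensing-route events with a pneumonia code on any claim within 7 days either side. Use one reconciled code list. Section 8.4.2.2 includes J22 and J86, which Annex 3.2 does not show, while the Annex has J95.4 and 997.31, which Section 8.4.2.2 does not.
3. Unless Section 8.9.2 already provides it, add a supportive Cox analysis of the primary outcome that does not count those events, and read it beside the severity-stratified results.

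Small and similar shares in the two groups would largely answer the point, as far as the codes can be trusted. Unequal shares would warn that a difference in exacerbations may partly be a difference in pneumonia.

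The cost is one filter, one set of counts and one extra model on claims already held. Because the filter relies on imperfect outpatient codes and may drop true exacerbations with coexisting pneumonia, possibly more with LABA/ICS, its result should be presented as helping to bracket the primary HR and not as a replacement for it.
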